7.3 Subject Identification

A unique subject identification code will be assigned when an individual subject is qualified for enrolment.

Subject identification details will be coded using subject's initials, subject case number and site number. Subject initials will be composed of the first letter of given name and first letter of last name (for example, AS for Adam Smith) and a three-digit sequential number. The investigator will complete subject identification on a confidential site log, which will be used for the purposes of traceability.

An example is provided below:

AS 101

In any case, other identification details (i.e. full names, phone numbers, etc.) will not be filled in any way in the CRF. The identification log will be kept in the study file only.

7.4 Inclusion Criteria

- Signed informed consent to participate in the study.
- Female and male subjects, ≥ 35 and ≤ 75 years of age at the time of enrolment

| | | |
|---------------------------------------------------------------------------------|------------------------------------------------------------------------|-----------------------|
|  | Treatment with the Evoke System for Facial and Submental Laxity | |
| | Protocol No: DO609886A SIRB ID: | Rev. Date: 29 Oct. 20 |

- If female, not pregnant, lactating and must be either post-menopausal, surgically sterilized, or using a medically acceptable form of birth control at least 3 months prior to enrolment (i.e., oral contraceptives, contraceptive implant, barrier methods with spermicide or abstinence).
- In addition, negative urine pregnancy test as tested before each treatment and at the last visit for women with childbearing potential (e.g. not menopause).
- General good health confirmed by medical history and skin examination of the treated area.
- Willing to have photographs and images taken of the treated areas to be used de-identified in evaluations, publications and presentations.
- The patients should be willing to comply with the study procedure and schedule, including the follow up visit, and will refrain from using any other aesthetic treatment methods for the last 6 months and during the entire study period.

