7.1 General Considerations

The study will recruit approximately 15 subjects per site, between the ages of 35-75, healthy adults with visible signs of aging, seeking skin laxity treatments.

Treatment areas include face, under chin

Eligible subjects will be screened. Investigators will screen subjects based on the inclusion/exclusion criteria described below after a written informed consent is signed.

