8.1 Screening and Baseline (Visit 1)

Screening visit will be performed in order to determine subject eligibility and to collect all required demographic and baseline clinical information. Study procedures and available treatment options, including the RF technology will be described in detail to the subject. Subject will be assured that the decision regarding participation in the study is strictly voluntary and that they are free to change their mind at any stage.

The subject will review the informed consent form and the study will be explained to the subject including all risks, potential benefits, procedures, visit requirements, and other alternative treatment options. If the subject qualifies and wishes to participate, he/she will complete the ICF with a signature and date. The original will be retained with subject's records and a copy will be provided to the subject. Subjects will then be screened for study eligibility according to inclusion and exclusion criteria.

The following Demographic and Baseline Measurements will be performed:

- Demographic data including gender, age, race, skin type (Fitzpatrick scale).
- ICF - Prior to any study procedures, informed consent will be obtained. When the subject fully understands the possible benefits and risks of the study, the subject will be asked to sign and date the informed consent form (ICF). The subject will be given a copy of the signed ICF.
- Subject ID - subjects will be assigned a study subject ID number.
- Medical History - A medical history will be obtained to determine if the subject meets the study criteria, including a list of all prescribed and over the counter medications taken within the previous 6 months will be recorded.
- Pregnancy Screen - Subjects who are capable of becoming pregnant will undergo a urine pregnancy test. This will be repeated prior to all treatments, and at the end of the study (last FU visit, 6-month FU).
- If the Screening and Treatment procedures are not conducted on the same day, the urine pregnancy test will be repeated on the first treatment day.
- Photography – Baseline photographs will be obtained using a consistent camera and subject placement settings with a digital imaging system.
- 3D Photography – Baseline 3D pictures will be obtained using 3D system. PI will ensure the same camera is used throughout the study.
- Up to 5 study participants be selected for baseline biopsy

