14.2 Statistical Analysis

Means, and standard deviations for each characteristic will be calculated. Paired sample t-test will be computed to assess changes in before treatment and follow-up scores. Statistical significance will be calculated and two-tail significance level of 0.05 will be used.

15. Data Management Plan

Case Report Forms will be retrieved by Monitors after verification and resolution of monitoring queries. Documents will be delivered to InMode Ltd onsite data management facility where forms will be logged in, and then data will be entered into a prepared Excel file.

Data will be entered using a double entry method and controlled by periodic and random validation check.

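### The screening lists do not require laxity, no baseline laxity grade is recorded, and the planned paired t-test suits only the 3D analysis, for which no metric is named

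*Combined protocol and SAP*

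**What the plan says.** **Population.** The synopsis and section 7.1 describe "healthy adults with visible signs of aging, seeking skin laxity treatments". Section 7.1 then states: "Investigators will screen subjects based on the inclusion/exclusion criteria described below after a written informed consent is signed". Section 8.1 likewise says that eligibility is judged on the inclusion and exclusion criteria.

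**Criteria.** Section 7.4 covers consent, age, pregnancy and contraception, health, photographs, and compliance including abstaining from other aesthetic treatment. Its only item about the skin is "General good health confirmed by medical history and skin examination of the treated area". Section 7.5 does not exclude a person without laxity.

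**Baseline.** Section 8.1 lists "Demographic data including gender, age, race, skin type (Fitzpatrick scale"), medical history, a pregnancy test, biopsies in up to 5 subjects, and two sets of images: "Baseline photographs will be obtained using a consistent camera and subject placement settings with a digital imaging system" and "Baseline 3D pictures will be obtained using 3D system". It lists no laxity or wrinkle grade.

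**Analysis.** The only inferential method in section 14.2 is: "Paired sample t-test will be computed to assess changes in before treatment and follow-up scores", two-sided at 0.05.

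**The concern.** Two gaps come from the same omission.

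First, the condition in the title appears in a descriptive sentence but not in the lists that decide entry. Visible aging is wider than laxity: the introduction (section 2) names laxity as one change among several, alongside pigmentation, roughness and telangiectasia. Seeking treatment is a wish, not an examination finding. Five sites could apply five thresholds, a monitor would have no criterion to check, and the report could not describe how lax the subjects were at entry.

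Second, a paired t-test needs the same quantity measured before and after. Most efficacy endpoints are collected only as change or satisfaction at follow-up. An analyst who follows section 14.2 literally would have to supply a before value that nobody measured.

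**Working it through.** The plan gives no power, effect size or success threshold, so it has no figure of its own to reproduce. The check sets the endpoints against the test and then adds illustrations.

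**1. Does each efficacy endpoint in section 6.1 have a before value?**

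| Endpoint | Recorded as | Before value |
|---|---|---|
| 1. Blinded photograph identification | correct or incorrect, 2 of 3 evaluators agreeing | none |
| 2. 3D analysis | comparison with baseline | baseline images exist; no metric named |
| 3. Investigator improvement, 0-4 | change rating at follow-up | none |
| 4. Subject improvement, 0-4 | change rating at follow-up | none |
| 5. Satisfaction, -2 to +2 | rating at follow-up | none |
| 6. Histology (optional, up to 5 subjects) | baseline and 3-month biopsy | sample exists; no score defined |

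Only the 3D analysis can carry the paired test across the whole study, and only once a metric is defined.

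**2. What happens if 0 is used as the before value for a 0-4 rating?** The scale has no category for worsening, so the mean is 0 only if every subject is rated 0. Suppose k of n subjects are rated 1 and the rest 0. The t statistic against 0 is then

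t = √[k(n − 1)/(n − k)].

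The synopsis lists 5 sites with about 15 subjects each, so n is about 5 × 15 = 75 (derived; no total is stated). Without site 3, which has no 1-month visit, n is about 60.

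- n = 75, k = 4: √(4 × 74/71) = 2.04, p = 0.045
- n = 60, k = 4: √(4 × 59/56) = 2.05, p = 0.045
- n = 15, k = 4: √(4 × 14/11) = 2.26, p = 0.041

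At n = 75, two-sided significance needs only 4/75 = 5.3% of subjects to be rated at the lowest improvement step.

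**3. What is chance for photograph identification?** If each evaluator guesses, the 2-of-3 rule is correct with probability 3 × 0.5³ + 0.5³ = 0.5. The natural reference is 50%, not a before score.

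**4. How much could unenforced entry dilute the result?** Let f be the fraction of subjects who cannot improve. The documents give no value for f, or for the rates and effects used here; all are assumptions.

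- Identification rate, 80% in subjects with laxity and 50% in the others: 0.8(1 − f) + 0.5f = 77%, 74% and 71% for f = 10%, 20% and 30%.
- The same with 90% in place of 80%: 86%, 82% and 78%.
- Paired t-test on a future 3D metric, n = 75, standardised effect d among those who can improve and unit SD in both groups: the effective value is (1 − f)d/√[1 + f(1 − f)d²]. For d = 0.3 this is 0.300, 0.238 and 0.148 at f = 0, 20% and 50%, with power 73%, 53% and 25%. For d = 0.5, power is 99%, 92% and 55%.

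**The case against.** **The population is stated.** The synopsis and 7.1 say whom the study will recruit, and 7.1 can be read as two steps: recruit that population, then apply the lists. This stands in part. A reader might infer from 7.4 that any healthy consenting person of the right age may enter, including people with nothing to improve. The documents do not support that: the intended population is described twice, and 7.4 and 7.5 contain many other restrictions. What remains is that the description is ungraded, is not laxity as such, and is missing from the lists used for screening.

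**A before measurement exists.** A reader might also infer that the paired test has no before value at all. That is too strong. The 3D analysis is one of the two primary objectives, baseline 3D images are required, and the same camera is to be used throughout. The gap there is the missing metric.

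**Laxity is not the only thing that can improve.** The primary objectives refer to skin appearance, and the stated device effects include wrinkle reduction. A subject with wrinkles and little laxity could improve. This stands, and it weakens the dilution figures, which treat such subjects as unable to change. Dilution would also understate the effect rather than create a false success, and no threshold is set for it to move.

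**An entry grade reused as the before score would mislead.** In a single-arm, open-label study, selecting on an investigator's grade and then re-measuring it invites regression to the mean and grading drift. This stands, and the fix keeps the two apart.

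**Conclusion.** The point holds as a gap of enforceability and of fit between endpoints and test, and it should be corrected. Sections 7.4 and 7.5 do not secure the titled population, and the baseline list in 8.1 leaves severity at entry unrecorded. The paired t-test in 14.2 cannot validly be applied to photograph identification, the 0-4 ratings or satisfaction. It could be applied to the 3D analysis once a metric is named.

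The firmest number is that 4 slight-improvement ratings among about 75 subjects, with all others 0, reach p = 0.045 against an implied 0. It depends only on the scale and the derived sample size, and it applies only if someone fills the gap that way; the plan does not say so. The dilution figures show direction and rough scale. The true fraction without laxity is unknown and may be small, because subjects come forward seeking laxity treatment.

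One limit: the Time and Events Schedule (Appendix 1) and the case report forms were not available. A baseline grade listed only there cannot be excluded, though it would not add the missing criterion to 7.4.

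**What to change.** - **Section 7.4:** add that visible facial and/or submental laxity is present at the baseline examination, as judged by the investigator.
- **Sections 6.1, 8.1 and 8.3:** name a graded laxity scale (the documents contain none). Have the blinded evaluators already planned score the baseline and follow-up photographs on it, singly, in random order and without knowing the visit. Keep this score separate from the investigator's entry judgement.
- **3D analysis:** name the numeric metric to be extracted at baseline and at each follow-up.
- **Section 14.2:** limit the paired t-test to the blinded laxity score and the 3D metric. Summarise the 0-4 ratings, satisfaction and photograph identification as proportions with confidence intervals, with identification compared with 50%.

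The cost is a few screen failures and some extra grading of photographs that will be taken anyway; no visit is added. The blinded laxity score is a new measure, so its place among the endpoints must be stated. Some regression to the mean will remain, because entry still depends on the baseline appearance and there is no control group. The report should acknowledge this when interpreting the change.

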7.5 Exclusion criteria

- Pacemaker or internal defibrillator, or any other active electrical implant anywhere in the body.
- Permanent implant in the treated area such as metal plates and screws, silicone implants or an injected chemical substance, unless deep enough in the periosteal plane.
- Current or history of skin cancer, or current condition of any other type of cancer, or premalignant moles.
- Severe concurrent conditions, such as cardiac disorders, epilepsy, uncontrolled hypertension, and liver or kidney diseases.
- Pregnancy and nursing.
- Impaired immune system due to immunosuppressive diseases such as AIDS and HIV, or use of immunosuppressive medications.
- Patients with history of diseases stimulated by heat, such as recurrent Herpes Simplex in the treatment area, may be treated only following a prophylactic regimen.
- Poorly controlled endocrine disorders, such as diabetes or thyroid dysfunction.
- Any active condition in the treatment area, such as sores, psoriasis, eczema, and rash.
- History of skin disorders, keloids, abnormal wound healing, as well as very dry and fragile skin.
- History of bleeding coagulopathies or use of anticoagulants in the last 10 days.
- Any surgery in treated area within 3 months prior to treatment.
- Six months delay is required if other recent treatments like light, CO2 laser or RF were performed on the same area.
- Use of Isotretinoin (Accutane®) within 6 months prior to treatment.
- Simultaneously participating in another investigator drug or device study or has completed the follow-up phase for the primary endpoint of any previous study less than 1 year prior to the first evaluation in this study.
- As per the practitioner's discretion, refrain from treating any condition that might make it unsafe for the patient

| | | |
|--------------------------------------------------------------------------------------------------------|------------------------------------------------------------------------|-----------------------|
|  I N M O D E | Treatment with the Evoke System for Facial and Submental Laxity | |
| | Protocol No: DO609886A SIRB ID: | Rev. Date: 29 Oct. 20 |

8. Study Procedures

The Time and Events Schedule is provided in Appendix 1.0.

8.1 Screening and Baseline (Visit 1)

Screening visit will be performed in order to determine subject eligibility and to collect all required demographic and baseline clinical information. Study procedures and available treatment options, including the RF technology will be described in detail to the subject. Subject will be assured that the decision regarding participation in the study is strictly voluntary and that they are free to change their mind at any stage.

The subject will review the informed consent form and the study will be explained to the subject including all risks, potential benefits, procedures, visit requirements, and other alternative treatment options. If the subject qualifies and wishes to participate, he/she will complete the ICF with a signature and date. The original will be retained with subject's records and a copy will be provided to the subject. Subjects will then be screened for study eligibility according to inclusion and exclusion criteria.

The following Demographic and Baseline Measurements will be performed:

- Demographic data including gender, age, race, skin type (Fitzpatrick scale).
- ICF - Prior to any study procedures, informed consent will be obtained. When the subject fully understands the possible benefits and risks of the study, the subject will be asked to sign and date the informed consent form (ICF). The subject will be given a copy of the signed ICF.
- Subject ID - subjects will be assigned a study subject ID number.
- Medical History - A medical history will be obtained to determine if the subject meets the study criteria, including a list of all prescribed and over the counter medications taken within the previous 6 months will be recorded.
- Pregnancy Screen - Subjects who are capable of becoming pregnant will undergo a urine pregnancy test. This will be repeated prior to all treatments, and at the end of the study (last FU visit, 6-month FU).
- If the Screening and Treatment procedures are not conducted on the same day, the urine pregnancy test will be repeated on the first treatment day.
- Photography – Baseline photographs will be obtained using a consistent camera and subject placement settings with a digital imaging system.
- 3D Photography – Baseline 3D pictures will be obtained using 3D system. PI will ensure the same camera is used throughout the study.
- Up to 5 study participants be selected for baseline biopsy
- Scheduling: Subjects will be scheduled to return for the baseline and first treatments visit within 3 weeks following the screening visit

8.2 Treatment (visits 1-3)

The Evoke treatment may occur on the same day of screening and baseline visit (or within 3 weeks following screening).

| | | |
|--------------------------------------------------------------------------------------------------------|------------------------------------------------------------------------|-----------------------|
|  I N M O D E | Treatment with the Evoke System for Facial and Submental Laxity | |
| | Protocol No: DO609886A SIRB ID: | Rev. Date: 29 Oct. 20 |

Enrolled subjects will undergo up to 3 successive bi-weekly (every 2 weeks) treatments (Tx.1, Tx.2 and Tx.3). Additional three (3) visits in the clinic will occur to follow-up the skin appearance changes and wrinkles reduction at visits 4,5 and 6 (4 weeks (except site #3) 12 weeks and 24 weeks following last treatment).

Treatment area: Treatment area will include face and under chin

Urine Pregnancy Test will be performed prior to each procedure.

Treatment procedure:

- Remove any jewellery in the treatment area
- Clean the Evoke Applicator with 70% alcohol. Detach electrodes from the mask frame (Cheek Applicator) using magnetic connection if needed.
- Test the Patient Call Button prior to each session. This will pause the treatment.
- Long and dense hairs may affect the treatment and should be shaved according to physician's discretion.
- Clean and dry the skin surface prior to applying the Applicators. Ensure there are no creams, lotions or sweat residue on the area to be treated.
- Treatment is performed in an upright sitting position. Ensure patient is comfortably seated.
- Make sure that the Applicator for the treatment corresponds to the device interface.
- Apply 2-4mm clear ultrasound gel (not oil) to the treatment area.
- Apply the Evoke Applicator (Chin or Cheeks) on top of the treatment area and adjust according to patient comfort.
- For Cheek Applicator:
 - Position the applicator-stabilizer (black metal hoop) on the back of the neck. Adjust the applicator according to patient anatomy. For a wider face, pull the stabilizer all the way out. For a narrow face, bring the stabilizer all the way in. Ensure that patient is seated upright when positioning the applicator on the head. Do not allow the patient to lean their head backward as the applicator will shift forward out of position. Patient head must remain upright throughout the entire treatment.
 - Secure the Applicator with 2 additional adjustable straps. One strap is positioned on the back of the head, and one across the top or the head.
- For Chin Applicator:
 - Place the Applicator on the under-chin area. Ensure that the electrodes are positioned on the soft tissue, not on bony areas. The position of the applicator should not be angled or tilted.
 - Secure the Applicator with the adjustable strap on the top of the head. Use additional silicone strap to secure the Applicator on the chin to prevent it from sliding to the neck.
 - There should be a complete coupling between all Applicator electrodes and the skin during the treatment session.
 - Adjust or reposition the Applicator if one or more electrodes do not have complete contact with the skin. In the event that the proper coupling between the electrodes and the skin cannot be achieved, due to patient anatomy or surface irregularities (such as

| | | |
|--------------------------------------------------------------------------------------------------------|------------------------------------------------------------------------|-----------------------|
|  I N M O D E | Treatment with the Evoke System for Facial and Submental Laxity | |
| | Protocol No: DO609886A SIRB ID: | Rev. Date: 29 Oct. 20 |

moles, scars, etc.), disable the specific electrode. Treatments can still be conducted if one or more of the electrodes are disabled.

- Provide patient with Patient Call Button and educate on proper use.
- Start with lower energy levels and gradually increase according to patient's comfort level. Set treatment time to desired treatment duration and press the Start button.
- Treatments can be paused by pressing the Pause button in the upper left corner of the screen.
- In case the Applicator needs to be readjusted or repositioned, pause the treatment, readjust the Applicator and restart the treatment. DO NOT readjust the Applicator when treatment is activated.
- The procedure should NOT feel hot or intolerable to the patient. If the patient complains of discomfort, immediately pause the treatment and inspect the area. Treatment can be continued with one or more of units disabled. Reduce RF power if required.
- Consequent cyclic electrodes activation during the procedure will be reflected on the screen.
- The treatment attendant should not leave the room after starting the treatment as it is important for the clinician to ensure that all Applicators reach the desired cut-off temperature and that the RF energy is maintained at the cut-off level. This should take approximately 2-5 minutes.
- During the procedure check Applicators position occasionally, as they can be shifted from the original placement.
- After the face is treated with Cheek Applicator (for approximately 45 min), if subject's anatomy allows the under-chin area will be treated with Chin Applicator for another 30-45 minutes using the same technique as with the Cheek Applicator.
- Typical response to treatment is erythema, slight edema.
- Subject will be asked to rate discomfort during the procedure. Discomfort will be assessed based on the Numerical Scale Response (NSR). The subject will be presented a scale with both words and numbers along a horizontal line and asked to make a mark along the scale. The subject will be asked to rate discomfort separately for cheeks and chin areas from 0 to 10, with 0 equalling no discomfort and 10 equalling the worst possible discomfort. A number is obtained by measuring up to the point the subject has indicated.
- After each treatment, observation, assessment and recording of adverse events will be conducted.

